10.2 OUTLINE OF STUDY PROCEDURES AND ASSESSMENTS

The first visit for this extension study is combined with the Month 6 visit of the main study. Therefore, the Month 6 assessments from the main study will not have to be duplicated at the start of the extension study. The study visit schedule is depicted in Figure 2 and the schedule of assessments is detailed in Appendix A and Appendix B.

* At the end of the 6-month follow-up, subjects with a BMD decrease from baseline of > 1.5% for lumbar spine and/or > 2.5% for total hip compared to main study baseline will have an additional DXA scan 6 months later.

Figure 2 : Schedule of Visits

All visits should take place at the end of the defined period (i.e. Month 7 visit should be scheduled at the end of Month 7, Month 8 visit should be scheduled at the end of Month 8, etc.). One month is defined as 28 days/4 weeks. All visit dates are calculated from the date the patient started treatment in the main study (Day 1 visit of 18-OBE2109-003 Edelweiss 3):

- Month 7 (Day 197), Month 8 (Day 225), Month 9 (Day 253), Month 10 (Day 281), Month 11 (Day 309) and Month 12 (Day 337) for the Treatment Period,
- Month 1 Extension FU (Day 365), Month 3 Extension FU (Day 421) and Month 6 Extension FU (Day 505) for the Follow-up Period.

A window of -3/+2 days is allowed for Month 7 visit, and of ± 3 days for each of the following visits during the Treatment Period. A window of ± 7 days/1 week is allowed for each visit scheduled during the Follow-Up Period.

The timing of events is shown in the Schedule of Assessments (Appendix A and Appendix B).

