10.2.1 Treatment Period

During the entire Treatment Period:

- the subject will use the same eDiary as during the main study. The eDiary should be completed daily, in the evening at approximately the same time, for use of provided/prescribed analgesics, uterine bleeding, pelvic pain, dyspareunia, dyschezia and daily function.
- the subject will take her daily dose of study medication at home except on the day of study visits where she will take her daily dose at site. There will be no IMP intake at the Month 12 visit. The last dose of study medication in this extension study will be the dose taken the day before Month 12 visit.
- the subject will be asked to bring her eDiary and her IMP kits at each visit to the site.
- the subject will receive contraception counselling at each visit.
- the subject will be provided/prescribed a limited quantity (as per Investigator's judgement) of standard doses of permitted analgesics as rescue medication for EAP for the duration of the study.
- the subject will receive calcium 500 to 1000 mg and vitamin D 400 IU supplementation which she will be advised to take daily (at least 4 hours from the intake of the study drug) until the end of the study. Intake should be recorded at each study visit in eCRF.
- AEs and concomitant medications will be recorded in the eCRF (excluding any provided/prescribed analgesics used for EAP will be recorded daily in the eDiary only).

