10.2.1.5 Study visit: Month 12 (Day 337 ± 3 days)

The following tests and evaluations will be performed :

- eDiary completion compliance check

- ePRO and ClinRO completion, ideally before any other procedures or assessments: EHP-30, EQ-5D-5L, PROMIS, mPGIS, PGIC, HRUQ, HRPQ, SSIQ andd PSIQ (mPGIS and PGIC must be completed last)
- Concomitant treatments recording
- AE recording
- Completion of the paper C-SSRS questionnaire (version for “already enrolled subjects” (see Appendix S) for patients responding to the C-SSRS for the first time during the study, or version “since last study visit” (see Appendix T) for patients for whom the C-SSRS was completed at the previous study visit)
- Final IMP accountability based on blisters
- ECG (at about the same time as but before the PK sample)
- Physical examination, including weight recording
- Vital signs (BP and heart rate)
- Urine pregnancy test
- Gynecological examination
- Manual breast examination (by palpation)
- TVUS of uterus
- Urinary protein dipstick
- Fasting (overnight) blood samples for haematology, coagulation parameters, chemistry, lipids, hormones (E2, LH, P4 and SHBG) and bone biomarkers
- PK sample (the time of dose administration on previous 4 days and time of PK sampling will be recorded)
- Endometrial biopsy, unless the endometrium thickness in TVUS is ≤ 5 mm, in which case no endometrial biopsy will be necessary (see section 10.4.5). Appropriate photo documentation of the endometrium thickness is mandatory.
- BMD assessed by DXA for femoral neck, hip and spine. DXA can be performed up to 10 days prior to the study visit which allows to get the DXA results ideally at the time of the Month 12 study visit at the latest.
- The subject will be verbally asked which treatment she believed she received during the Treatment Period in the extension study. The answer will be recorded in the eCRF.
- Contraception dispensing (if applicable) and counselling
- Prescribe/dispense permitted analgesics as rescue medication
- Dispense calcium and vitamin D supplementation

An additional question will be asked to the subject about the burden of filling in the eDiary (0 = not at all a burden, 10 = very much a burden). The answer will be recorded in the eCRF.

The Month 12 study visit constitutes the end of the Treatment Period pertaining to this extension study.

The subject will continue in the post-treatment 6-month Follow-Up (FU) Period.

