10.2.2.1 Study visit: Month 1 Extension FU (Month 1 ExFU)

Month 1 ExFU visit should be scheduled on Day 365 ± 7 days after main study Day 1 (or 28 days ± 7 days after last IMP intake for early discontinued subjects).

The following tests and evaluations will be performed at Month 1 ExFU visit:

- eDiary completion compliance check
- ePRO completion, ideally before any other procedures or assessments: mPGIS and PPGIC (must be completed last)
- Concomitant treatments recording
- AE recording
- Completion of the paper C-SSRS questionnaire (version for “already enrolled subjects” (see Appendix S) for patients responding to the C-SSRS for the first time during the study, or version “since last study visit” (see Appendix T) for patients for whom the C-SSRS was completed at the previous study visit)
- ECG
- Vital signs (BP and heart rate)
- Urine pregnancy test and contraception dispensing and counselling
- Urinary protein dipstick
- Blood samples for haematology, coagulation parameters, chemistry, hormones (E2, LH and P4)
- Endometrial biopsy only if diagnosis at Month 12 was different than “benign endometrium” or if no endometrial biopsy was done at Month 12 (see section 10.4.5).
- Prescribe/dispense permitted analgesics as rescue medication
- Dispense calcium and vitamin D supplementation

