5.2. Data Conventions

5.2.1. Last extension treatment administration date, End of extension Study date and Period definitions

The last extension treatment administration date will be defined as the date from the treatment termination reported in the extension period eCRF page. If this date is missing, the last date with a drug intake in the eDiary that is inferior or equal to Month 12 visit or the last available date with a drug intake in the eDiary if the subject discontinued the extension treatment will be used.

For subjects who entered the extension, the end of the extension study date will be the last assessment date in the extension study defined as last assessment recorded in the eCRF (excluding end date of adverse events and concomitant medications) or ediary date (excluding drug intakes recorded after last extension treatment administration date). This will not necessarily be the same date as last assessment date as recorded in the eCRF.

For each 28-day period prior to Month X (except Month 12), the end of the period will be defined as the Month X visit date. If subject discontinued prior to Month X, the end of the period will be the date from the treatment termination of extension period eCRF page or the last date with a drug intake in the eDiary if missing. If the subject missed the Month X visit (but did not discontinue), the subject might still have filled the diary during that time: the theoretical Month X date will be used to define the end of the 28-day period. The theoretical Month X is defined with respect to Day 1 as Month X= Day 1+ $28^{*}X$.

For the 28-day period prior to Month 12, the end of the period will be defined as the last extension treatment administration date.

Note:

For Adverse Events, Concomitant Medications and Daily diaries data collected on the Month 6 date will be part of the extension for subjects entering the extension study.

For Adverse Events, Concomitant Medications and Daily diaries, data collected on the Month 12 date will be part of the Extension Follow-up period for subjects entering the Extension follow-up period.

The extension treatment period will be defined as Month 6 up to (Month 12 date -1) or treatment discontinuation date.

The extension follow-up period will be defined as the Month 12 date or (treatment discontinuation date+1) up to the extension follow-up end date (for subjects who entered the extension follow-up).

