6.4.3. Secondary/other/exploratory analysis

All secondary efficacy endpoints will be summarized by descriptive statistics for each treatment group, for each time point, including summaries of change from baseline when applicable.

Values for all endpoints that are collected daily using the eDiary (from Section 6.4.3.1 to Section 6.4.3.24) will be based on the 28 calendar days immediately prior to and including the day of the corresponding visit or prior to and including the last treatment administration date for Month 12, or the 28 calendar days immediately prior to and including the last dose date for subjects who discontinue treatment prior to the visit in question (or fewer if treatment is stopped less than 4 weeks after first dose date), in order to estimate the treatment effect while under treatment. The last 28 days on treatment will be used at all subsequent scheduled visits for those discontinued subjects. Descriptive summaries for each 28-day period will be performed in two ways however:

- Once including only values of 28 days prior to Month X, i.e. using the last 28 days prior to Month X eCRF visit date for subjects who have not discontinued up to that month. If subjects discontinued prior to Month X the corresponding value will be missing from the summary at Month X;
- Once applying the while on treatment strategy, i.e. using the last 28 days prior to Month X eCRF visit date for subjects who have not discontinued up to that month, and for subjects who discontinued prior to Month X, the last 28 days prior to treatment discontinuation will be used. For all subsequent timepoints (Month X+1, etc.) the same last 28 days prior to treatment discontinuation will be used.

Corresponding baseline values will be calculated based on the two baseline menstrual cycles, which may not be exactly 28 days each.

The values for other endpoints (monthly and 3-monthly questionnaires from Section 6.4.3.25 to Section 6.4.3.32) are defined as the value at the corresponding visit or value falling into the corresponding visit window as described in section 5.5. For these other endpoints, descriptive summaries by visit will be performed in two ways, once including values at the corresponding visit or value falling into the corresponding visit window as described in section 5.5, and once applying the while on treatment strategy, i.e., including values from the discontinued visits at each next scheduled visit.

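### Read literally, the 28-day diary look-back at Month 1 ExFU is not cut at the end of treatment, so on allowed visit dates 0 to 9 of its 28 days can be on-treatment days

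*SAP*

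**What the plan says.** SAP 6.4.3 states that daily-diary values "will be based on the 28 calendar days immediately prior to and including the day of the corresponding visit". It gives another anchor in two cases only: Month 12 (the last treatment date) and women who discontinue treatment, whose last 28 treated days are carried to all later visits in one of the two planned summaries and who are missing in the other.

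SAP 5.2.1 fixes where a period ends: "For each 28-day period prior to Month X (except Month 12), the end of the period will be defined as the Month X visit date". On the split between treatment and follow-up it says: "The extension follow-up period will be defined as the Month 12 date or (treatment discontinuation date+1) up to the extension follow-up end date". It adds that diary "data collected on the Month 12 date will be part of the Extension Follow-up period for subjects entering the Extension follow-up period". It does not say that a 28-day look-back is shortened at that boundary.

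The visit dates come from the protocol. Section 10.2.1.5 allows Month 12 on Day 337 ± 3. Section 10.2.1 says: "The last dose of study medication in this extension study will be the dose taken the day before Month 12 visit". Section 10.2.2.1 says: "Month 1 ExFU visit should be scheduled on Day 365 ± 7 days after main study Day 1". Both visits are therefore counted from main-study Day 1, and the second is not tied to the date on which Month 12 actually took place.

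**The concern.** Month 1 ExFU is the first off-treatment point for the diary endpoints. When Month 12 is late and Month 1 ExFU is early, the two visits are less than 28 days apart, and the look-back reaches into the dosing period. Those days are already in the Month 12 window, so the same entries would describe both the treated and the untreated state. If symptoms are milder on treatment, the Month 1 ExFU value is pulled towards the Month 12 value and the effect looks more lasting after stopping than it is.

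**Working it through.** **The plan's schedule.** With a 28-day month, the visit day is 1 + 28 × X. For X = 12 this gives 337 and for X = 13 it gives 365, which match the protocol's Month 12 and Month 1 ExFU.

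**Overlap formula for completers.** Let Month 12 fall on Day 337 + a (a from −3 to +3) and Month 1 ExFU on Day 365 + b (b from −7 to +7).

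- Last dose: Day 336 + a.
- First day of the Month 1 ExFU look-back: 365 + b − 27 = Day 338 + b.
- Treated days in the look-back: max(0, (336 + a) − (338 + b) + 1) = max(0, a − b − 1).

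| Month 12 | Month 1 ExFU | Look-back | Treated days |
|---|---|---|---|
| Day 337 | Day 365 | 338–365 | 0 |
| Day 340 | Day 365 | 338–365 | 2 |
| Day 337 | Day 358 | 331–358 | 6 (21%) |
| Day 340 | Day 358 | 331–358 | 9 (32%) |

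In the last row the treated days are Days 331–339. The Month 12 window is then Days 312–339, so all nine are used twice.

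**All allowed pairs.** There are 7 × 15 = 105. Overlaps of 1 to 9 days occur in 7, 7, 7, 6, 5, 4, 3, 2 and 1 pairs, which is 42 pairs (40%); 15 pairs (14%) overlap by 5 days or more. The overlap days total 161, so the mean is 161/105 = 1.5 days, or 5.5% of the window. The percentages describe women only if all pairs are equally likely, which is an assumption.

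**Later visits.** The earliest Month 3 ExFU is Day 421 − 7 = 414, with a look-back from Day 387. The earliest Month 6 ExFU is Day 505 − 7 = 498, with a look-back from Day 471. Both start after Day 339, so the overlap is zero.

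**Effect on a value.** For a mean over all 28 days, 9 treated days leave 19/28 = 68% of the change. With assumed means of 0.5 on treatment and 1.5 off, the result is (9 × 0.5 + 19 × 1.5)/28 = 1.18, a rise of 0.68 instead of 1.0. This fraction does not carry over to DYS or NMPP, because SAP 6.4.2.1 averages DYS over bleeding days and NMPP over non-bleeding days:

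- NMPP can be diluted more. If all 9 treated days were free of bleeding and 5 off-treatment days had bleeding (assumed), the treated share is 9/23 = 39%.
- DYS can be diluted less. Treated days without bleeding add nothing to the mean when bleeding occurs elsewhere in the window.

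**A discrepancy that shifts the maximum.** Protocol 11.2 describes dosing up to and including Month 12, while 10.2.1 puts the last dose on the day before. On the 11.2 wording the maximum overlap is 10. The two sections need to be reconciled.

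**The case against.** The best reply is that 6.4.3 never names an ExFU visit. Its stated aim is the effect under treatment, and its two summary methods are written for Month X and for discontinuation. SAP 5.2.1 also assigns diary days to periods, and on that split the days before Month 12 are treatment data. A programmer might cut the window without being told. This stands to the extent that the gap is an ambiguity and not a proven double count. It does not close the gap. The endpoints are defined at each scheduled assessment, the diary runs daily to Month 6 ExFU (Protocol 10.2.2), and 6.4 applies the efficacy analysis to the Follow-up Extension Analysis Set. The only window rule on offer is the general one.

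A second reply is that SAP Table 2 dates Month 1 ExFU at Month 12 + 28. With ± 7 days on that basis the maximum is 6. But the protocol's scheduling rule allows 9.

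A third is that little depends on this. No hypothesis tests are planned, and the primary and secondary efficacy objectives concern the last 28 days of treatment. That stands and limits the weight of the point.

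A fourth is that simply shortening the window harms the day-count endpoints. Pain days, analgesic days, bleeding days and missed-work days are unscaled counts per 28-day period. Cutting to 19 days can only lower them, and 6.4.3.21 fixes its denominator at 28. This also stands, and the fix has to deal with it.

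**Conclusion.** The point holds as a gap in the SAP affecting one descriptive time point. For completers with protocol-compliant visits and the last dose on the day before Month 12, 0 to 9 of the 28 diary days at Month 1 ExFU can be treated days, with zero at nominal dates and a mean of 1.5 under equally likely pairs.

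A reader might infer that the return of pain is understated, or that it is understated by up to a third across the diary endpoints. The documents do not support either. Nine days is the single worst of 105 pairs. The direction rests on pain being lower on treatment, and the documents give no follow-up pain values. The dilution also differs between all-day means, DYS, NMPP and counts. What can be said is that the return of symptoms at Month 1 ExFU can be understated, by an unknown amount.

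Early discontinuers need the same rule for a different reason. SAP section 7 widens the follow-up set so that they are followed for efficacy. Yet the 6.4.3 carry-forward, taken literally, gives them 28 of 28 treated days at ExFU visits, or a missing value in the other summary.

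**What to change.** State in SAP 5.2.1 and 6.4.3 that:

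- for ExFU visits the diary window is the 28 days up to and including the visit, starting no earlier than the day after the last extension dose;
- mean scores are taken over that window, shortened where necessary;
- day-count endpoints are scaled to 28 days or reported as a proportion of observed days, and the denominator in 6.4.3.21 is the actual window length;
- the minimum stays at 12 completed entries;
- this rule, and not the on-treatment carry-forward, applies at ExFU visits.

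The SAP already accepts a window shorter than 28 days for women who stop within four weeks of their first dose, so the idea is not new to it.

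The cost is up to 9 fewer diary days for some women, and a small amount of extra programming. On compliant dates with the last dose on the day before Month 12, at least 19 days remain. Twelve entries are then 12/19 = 63% of the shortest window instead of 12/28 = 43%, so a few more women could miss the minimum. No new data are needed.

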10.7.2 Subject Withdrawal

Subjects will be informed that they have the right to withdraw from the study at any time, without prejudice to their medical care, and that they are not obliged to state the reason(s). Any withdrawal must be fully documented in the eCRF exit form.

The Investigator may withdraw a subject at any time if this is considered to be in the subject's best interest.

In addition, the Sponsor could make a decision to temporarily or permanently discontinue the study for safety, ethical, compliance or other reasons. In this case, the subject's participation may be ended prematurely without asking for her consent.

In case of early discontinuation, the subject will be instructed to complete the relevant eDiary questionnaires as soon as possible upon treatment discontinuation.

Withdrawal during Treatment Period:

Subjects discontinuing participation in the study during the Treatment Period should undergo the procedures required at Month 12, except the DXA in case of discontinuation before Month 9 visit. These subjects will enter the 6-month Follow-Up Period and will continue daily eDiary recording for 6 months and up to Month 6 ExFU visit in order to continue to collect efficacy and safety data.

PK sampling is not required if the subject had no IMP administration the day prior to the withdrawal visit.

Withdrawal during Follow-Up Period:

Subjects discontinuing participation in the study during the Follow-Up Period should undergo the procedures required at Month 6 ExFU visit, which includes completion of all ClinRO and ePRO questionnaires, except the DXA in case of discontinuation before Month 3 ExFU visit.

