7. CHANGES TO PLANNED ANALYSES

The Follow-up Extension Analysis Set, defined in protocol as:

All subjects from the main study who completed the 6 months of treatment in the extension study and who entered the Post-Treatment Follow-Up Period. Subjects will be analyzed according to randomized treatment.

Is changed to:

All subjects from the main study who entered the extension study and received at least one dose of study drug with the exception of subjects whose Month 6 assessment subsequently met any of the discontinuation criteria, and who entered the Post-Treatment Follow-Up Period. Subjects will be analyzed according to randomized treatment.

The rationale for this modification is that subjects that entered the Follow-up period, even if they did not complete the 6 months of extension treatment should be followed up for efficacy.

SAP Version	Update description	SAP Section	Reason
V2.0	Assessments from Local Laboratories (due to Covid-19 situation) will be excluded from summary tables of laboratory data	Section 6.6.3	Local laboratories may not have comparable normal ranges, thus it does not make sense to pool them with central laboratory data in numeric summaries.
V2.0	Biopsy assessments from Local Laboratories (due to war situation in Ukraine) should be flagged in listings. Information is available in Data Management Closed Queries File.	Section 6.6.8.1	Due to war situation in Ukraine, there were some Biopsies assessed locally. This information should be incorporated in listings.
V2.0	Addition of listings for PAP Smear for both abnormality and diagnosis information.	Section 6.6.8.3	PAP Smear listings were missing from original SAP Version.
V3.0	All protocol deviations related to a particular subject will be presented in the data listings.	Section 4.2	There were PD records which had missing subject ID and thus were not

Updates from SAP Amendments since SAP V1.0 are summarized in the table below:

CRS-BS-TP-000005 V 2.0

Page **75** of **99**

Kissei / Cytel Confidential: This is a controlled document and shall not be changed, saved, copied or reproduced by any unauthorized person.

			related to any particular subject. These records were excluded in the listings.

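### For daily-diary endpoints the SAP's early-discontinuation rule has no follow-up exception, so read literally it keeps early stoppers' post-treatment diaries out of the follow-up summaries

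*SAP*

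**What the plan says.** SAP 6.4.3 sets one value rule for all endpoints built from the daily eDiary (6.4.3.1 to 6.4.3.24). The default is the 28 days up to the visit. For women who stop treatment before the visit in question it is the 28 days up to the last dose, and then: "The last 28 days on treatment will be used at all subsequent scheduled visits for those discontinued subjects".

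Two summaries follow for each period:

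- Observed only: "If subjects discontinued prior to Month X the corresponding value will be missing from the summary at Month X".
- While on treatment: "For all subsequent timepoints (Month X+1, etc.) the same last 28 days prior to treatment discontinuation will be used".

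SAP 5.2.1 anchors the period in the same way: "If subject discontinued prior to Month X, the end of the period will be the date from the treatment termination of extension period eCRF page". None of these sentences distinguishes treatment visits from follow-up visits.

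Three other places assume that post-treatment diaries from early stoppers will be used:

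- Protocol 10.7.2: women who withdraw during treatment "will continue daily eDiary recording for 6 months and up to Month 6 ExFU visit in order to continue to collect efficacy and safety data".
- SAP 5.2.1: the extension follow-up period for these women starts the day after discontinuation.
- SAP section 7: the Follow-up Extension Analysis Set was widened beyond completers because "subjects that entered the Follow-up period, even if they did not complete the 6 months of extension treatment should be followed up for efficacy".

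SAP 6.4 plans efficacy summaries on that set.

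**The concern.** A follow-up efficacy table should show what happens to pain once the drug is stopped. Under the stated rule, early stoppers supply no off-drug diary information to it. In the observed-only version they drop out, so the diary summaries rest on women who completed treatment. In the while-on-treatment version their on-treatment values are averaged, at visits one to six months after the last dose, with completers' real off-drug values.

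Dysmenorrhea shows the risk most clearly. SAP 6.4.2.1 scores it as zero when no bleeding day is recorded in the period. A woman without bleeding on treatment would carry a score of zero into all three follow-up visits, even if menses and pain had returned. If pain does return off drug, the carried version understates that return.

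**Working it through.** **1. Reproduce the visit days.** Protocol 10.2 gives Month 1, 3 and 6 ExFU as Days 365, 421 and 505. With 28-day months counted from Day 1, Month 12 is 1 + 28 × 12 = Day 337. Adding 28, 84 and 168 gives 365, 421 and 505, an exact match.

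**2. Compare the two windows for an early stopper.** Let *s* be the day of the last dose. SAP 5.5, Table 2, times her ExFU visits at *s* + 28, *s* + 84 and *s* + 168. The rule uses days *s* − 27 to *s*. The 28 days up to each actual visit run from *s* + 1, *s* + 57 and *s* + 141.

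| Last dose Day 225 | Visit day | Window under the rule | 28 days up to the visit | Days shared |
|---|---|---|---|---|
| Month 1 ExFU | 253 | 198-225 | 226-253 | 0 |
| Month 3 ExFU | 309 | 198-225 | 282-309 | 0 |
| Month 6 ExFU | 393 | 198-225 | 366-393 | 0 |

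The overlap is also 0 for last doses on Days 197, 253, 281 and 309.

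**3. Check for ambiguity between tables.** In the same example, Day 253 is both Month 1 ExFU and theoretical Month 9, and Day 309 is both Month 3 ExFU and theoretical Month 11. The text does not tell a programmer which value goes into which table.

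**4. Check the visit questionnaires.** These also have two summaries in SAP 6.4.3. The while-on-treatment version carries the withdrawal-visit value forward. The other uses the value recorded at the visit or falling in its window, and does not blank discontinued women. Table 2 gives early stoppers' ExFU visits a place, and SAP 6.4.3.26, 6.4.3.27, 6.4.3.31 and 6.4.3.32 report through Month 6 ExFU. EHP-30, with its pain scale, is scheduled at Months 3 and 6 ExFU. Real off-drug questionnaire values can therefore enter.

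**5. Size.** If a share *p* of the women in the summary are early stoppers, carry-forward lowers the ExFU mean by *p* × (their off-drug mean − their on-treatment mean). The documents supply neither *p* nor either mean.

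**6. Test the replacement window.** Month 1 ExFU may fall 7 days early. The visit is then at *s* + 21 and its 28 days run from *s* − 6, so 7 of them (*s* − 6 to *s*) are still on treatment. Dropping those leaves 21 days, above the 12-day minimum in SAP 6.4.3.

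**The case against.** The strongest reply is that carry-forward was never meant for follow-up. The two diary summaries are written for Month X, and SAP 5.2.1 counts that from the start of the main study: "The theoretical Month X is defined with respect to Day 1 as Month X= Day 1" plus 28 days per month. ExFU visits have other names and another anchor. The stated purpose is "in order to estimate the treatment effect while under treatment", which cannot describe an off-drug visit. Several endpoint paragraphs, for example 6.4.3.1 and 6.4.3.18, tie the last-dose window to stopping before Month 12.

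This is a fair reading and may be what was intended. It does not remove the words about all subsequent scheduled visits, and ExFU visits are scheduled visits. It also leaves early stoppers without any stated ExFU diary window, so the same clarification is needed.

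Three stronger inferences are tempting, and the documents do not support them:

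- *Early stoppers' post-treatment data never reach a follow-up table, and the section 7 change achieves nothing.* The observed-visit questionnaire summary uses their actual ExFU values. SAP 6.6.8.5 uses the post-treatment bleeding diary for time to first menses. SAP 6.2.1 lists raw and derived data.
- *The questionnaire rule has the same effect as the diary rule.* That is true only of its while-on-treatment summary.
- *The bias can be quantified.* Assume 10-20% early stoppers and dysmenorrhea scores of 0.5 on and 1.8 off treatment: 0.10 × 1.3 = 0.13 and 0.20 × 1.3 = 0.26 points. None of these inputs is in the documents. The 1.10 responder threshold is no yardstick either, because it applies to change within one woman and not to a group mean.

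The stakes are also limited. The study is descriptive, with no formal tests, and its efficacy objectives concern the last 28 days of treatment up to Month 12.

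**Conclusion.** The point holds for daily-diary endpoints at Months 1, 3 and 6 ExFU. Followed literally, SAP 6.4.3 and 5.2.1 give early stoppers either no value or one from a window sharing 0 of 28 days with the real one at nominal visit timing. This conflicts with the SAP's own reason for enlarging the Follow-up Extension Analysis Set and with the protocol's reason for continuing the diary.

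The direction of any error, toward hiding symptom return in the carried version, assumes that pain is worse off drug than on it. Its size is unknown. The Month 12 primary endpoint is unaffected, because its window ends at the last dose by design. The SAP should be corrected on this point, but the trial's main conclusion does not depend on it.

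**What to change.** In SAP 5.2.1 and 6.4.3:

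1. State that carry-forward of the last on-treatment diary window, and of withdrawal-visit questionnaires, applies only to visits up to Month 12.
2. For Months 1, 3 and 6 ExFU, define the diary value for every woman in the Follow-up Extension Analysis Set as the 28 days up to the actual ExFU visit, counting only days after the last dose, with no carry-forward.

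The cost is about two sentences and one condition in the diary derivation. The protocol already has the data collected.
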